## **5.5.2 Secondary Endpoints Analyses**

### **Physical function**

- Proportion of participants with a worsening in TUG time from baseline at 12 and 24 week study visits, and at any time up to 52 weeks will be summarized.
- TUG time (secs) and percent change from baseline will also be summarized by metastatic/non-metastatic CRPC status, pain (yes, no pain), and opioid use (yes, no opioid use).
- At each assessment, status of TUG time will be summarized as the categories of improved, stable or worsened.
- Time to worsening in TUG time will be defined as time from randomization (or time from first dose for participants in the lead-in phase) to the first date a participant had a worsening. Time to worsening in TUG time will be summarized using Kaplan-Meier methodology, and a comparison between the two arms in the randomization phase will be made using a two-sided, stratified log-rank test, stratified by Age (<75, ≥75). The hazard ratio as well as its 95% CI will be presented using a stratified Cox regression model. An unstratified analysis will also be performed. The Kaplan-Meier plots will be provided for both stratified and unstratified analyses.
- Similar to the primary endpoint, the proportion of participants with a decline of at least 1 point in SPPB total score at 12 and 24 week study visits and at any time up to 24 and 52 weeks will be summarized. SPPB

will be analyzed by age (<75, ≥75), metastatic state (nmCRPC, mCRPC), Pain (yes, no pain), opioid use (yes, no opioid use).

### Daily Activity

- Descriptive statistics on mean change and percent change from baseline in daily activity, measured as counts per minute (CPM), will be provided for both lead-in at 12 and 24 weeks and randomization phase at 12, 24 and 52 weeks. Subjects must provide at least 2 out of 7 days of data prior to the visit, each day containing ≥10 awake hours, to be considered eligible for analysis. For each epoch, counts from the X, Y and Z axes will be converted to a single measure per the vector magnitude =

$$\sqrt{(axis\ 1)^2 + (axis\ 2)^2 + (axis\ 3)^2}$$

CPM for each valid day is defined as ‘awake wear-filtered total vector magnitude counts’ divided by ‘awake wear minutes’. A subject’s CPM at each visit is the average of daily CPM.

- CPM will also be analyzed by age (<75, ≥75), metastatic state (nmCRPC, mCRPC), pain (yes, no pain), and opioid use (yes, no opioid use) in both phases. In the randomization phase, model-based least squares means on percent change from baseline in CPM will be reported for treatment group, adjusting for baseline CPM, age (<75, ≥75), metastatic state (nmCRPC, mCRPC), pain (yes, no pain) and opioid use (yes, no opioid use).
- Because of the skewed nature of CPM data, summary statistics will also be provided for log-transformed CPM. For summary statistics by visit, calculations are done on the log scale, and then back-transformed at the end. For % change from baseline, the back-transform for (LS)mean (95% CI) =  $100 \times [\exp(\text{LS)mean change from baseline (95\% CI) in natural logarithm}) - 1]$ .
- For the randomization phase, treatment arms will be compared at each visit using 2-sample t-test, mean change difference (SE), 95% CI and p-value of darolutamide vs. enzalutamide will be provided.
- The percentage of time at each visit that CPM fall into the following categories will be summarized for the lead-in phase: Sedentary (0-99), Light (100-1951), Moderate (1952-5724), Vigorous (5725-9498), Very vigorous (9499-∞). Also mean change and percentage change from

baseline will be summarized for percentage of time spent in each of the aforementioned categories.

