
The secondary objectives of this study are to:
 
 • Compare the effects of treatment with darolutamide vs enzalutamide on physical function, as assessed by the TUG test at 12 and 24 weeks, and by 52 weeks. • Compare the effects of treatment with darolutamide vs enzalutamide on physical function as assessed by the SPPB test at 12 and 24 weeks, and by 24 and 52 weeks. • Assess the effects of treatment with darolutamide vs. enzalutamide on daily activity as assessed by accelerometry at 12 and 24 weeks, and by 24 and 52 weeks. • Compare the effects of treatment with darolutamide versus enzalutamide on cognitive function as assessed by HVLT-R, TMT, COWA, and FACT-Cog • Compare the effects of treatment with darolutamide versus enzalutamide on fatigue as assessed by the BFI • Compare the effects of treatment with darolutamide vs. enzalutamide on depression as assessed by the PHQ-9 • Evaluate safety, including AEs of interest, of participants treated with darolutamide vs. enzalutamide 
 • Evaluate the effect of treatment with darolutamide or enzalutamide on PSA, survival status, and exposure 	
Physical Function:
 
 • Proportion of participants with an increase of at least 1 second in TUG time at 12 and 24 weeks and during the 52 weeks from baseline. • Time to worsening (increase of at least 1 second) in TUG time • Proportion of participants with a worsening in SPPB total score at 12 and 24 weeks and during the 24 weeks and 52 weeks from baseline. Worsening is defined as a decline of at least 0.5 points in SPPB total score. 
Daily Activity:
 
 • Mean change from baseline in daily physical activity at 12 and 24 weeks, and during the 24 weeks and 52 weeks from baseline. • Mean change from baseline in accelerometer-assessed proportion of time spent in light to vigorous physical activity based on a threshold of >100 activity counts per minute at 12 and 24 weeks, and during the 24 weeks and 52 weeks from baseline. 
Cognitive Function:
 
 • Proportion of participants with a decline in cognitive function during the 24 weeks and 52 weeks from baseline, as assessed by HVLT-R, TMT, and COWA. See Table 8–1 for the definition of decline for each test. • Proportion of participants with a decline using a selected domain of FACT-Cog. Decline is defined as a decrease of >10 points during the 24 weeks and 52 weeks from baseline. 
Fatigue:
 
 • Proportion of participants with a worsening of fatigue during the 24 weeks and 52 weeks from baseline. Worsening is defined as an increase of at least 1 point in worst level of fatigue from baseline by 24 weeks and 52 weeks (based on item 3 of the BFI). • Proportion of participants with an increase of at least 1 point in fatigue interference by 24 weeks and 52 weeks from baseline (based on items 4A-F of the BFI).

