Secondary	
Physical Function
 
 Proportion of participants with an increase of at least 1 second in the TUG time from baseline at 12 and 24 weeks, and by 52 weeks will be summarized similar to the primary endpoint. Time to worsening (increase of at least 1 second) in TUG time will be defined as time from randomization (or time from first dose for participants in the lead-in phase) to the first date a participant had an increase of at least 1 second or more from baseline. Time to worsening in TUG time will be summarized using Kaplan-Meier methodology, and a comparison between the two arms will be made using a two-sided, stratified log-rank test, stratified by IWRS strata. The hazard ratio as well as its 95% CI will be presented using a stratified Cox regression model. An unstratified analysis will also be performed. Similar to the primary endpoint, the proportion of participants with a decline of at least 0.5 points in SPPB total score at 12 and 24 weeks and by 24 and 52 weeks will be summarized. 
Daily Activity
 
 Mean change from baseline in daily activity will be calculated for each treatment arm at 12 and 24 weeks, and by 24 weeks and 52 weeks and will be compared using two sample t-test. 95% CI will be presented. Mean change from baseline in accelerometer-assessed proportion of time spent in light to vigorous physical activity based on a threshold of >100 activity counts per minute at 12 and 24 weeks and by 24 and 52 weeks will be summarized. 
Additional daily activity parameters based on accelerometry data may be explored and details will be provided in the SAP.
 
Cognitive Function
 
 The proportion of participants with a decline in cognitive function by 24 and 52 weeks as assessed by HVLt-R, TMT, and COWA, will be summarized similar to the primary endpoint. At each assessment, the change in score from baseline will be calculated and the status of cognitive function will be categorized as improved, stable, or declined using the Reliable Change Index (RCI) as shown below. Each test will be assessed individually.

Endpoint	Statistical Analysis Methods															

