### 5.5.1 Primary Endpoint Analyses

The primary variable in this study is the proportion of participants with a worsening in TUG time during the 24-week period from baseline, using the best TUG time out of the measured assessments during study visits (two or

three assessments). Worsening is defined as an increase of at least 1 second in TUG time from baseline.

The proportion of participants with a worsening in TUG time and the (exact) 95% CIs will be summarized by treatment arm. A comparison between treatment arms will be made using Cochran-Mantel-Haenszel (CMH) test adjusting for Age (<75, ≥75). A sensitivity analysis will be provided by replacing missing TUG times with ≥ 1 second increase. Primary endpoint (worsening in TUG) analysis will be performed by age (<75, ≥75), metastatic state (nmCRPC, mCRPC), Pain (yes, no pain), and opioid use (yes, no opioid use). Information on pain and opioid use will be retrieved from an examination of medical history and prior medication CRFs.

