### **5.5.8 Concomitant and Prior Medications**

Prior and Concomitant medications are coded using the World Health Organization Drug Dictionary Enhanced (WHO-DDE version 2020Mar or higher), tabulated by drug class and term, and summarized by frequency and percentage of patients. Patients are counted only once in each summary category (e.g. drug class or term).

Prior medications are defined as medications taken within 12 weeks and stopped before treatment Day 1. Concomitant medications are defined as ongoing at treatment Day 1 or taken on Day 1 or thereafter up to the last dose of treatment plus 30 days. Prior and concomitant medications are summarized within each category separately and listed.

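### The only specified arm comparison on accelerometry CPM is an unadjusted t-test, while the planned baseline-adjusted model yields no between-arm contrast; the test is valid, but precision may be lost

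*SAP*

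**What the plan says.** Protocol 9.4.2 says that mean change in daily activity will be calculated by arm "and will be compared using two sample t-test". SAP 5.5.2 (Daily Activity) follows it: "treatment arms will be compared at each visit using 2-sample t-test, mean change difference (SE), 95% CI and p-value of darolutamide vs. enzalutamide" are to be given for the randomized phase. The line does not say whether the change is in untransformed or log CPM. Untransformed is the natural reading.

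The same SAP section plans a second randomized-phase analysis: "model-based least squares means on percent change from baseline in CPM will be reported for treatment group, adjusting for baseline CPM", together with age group, metastatic status, pain and opioid use. The output named is a mean for each arm. No arm difference, interval for a difference or p-value is specified from this model. The SAP calls CPM skewed, and its back-transform formula puts percent change on the natural-log scale.

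The protocol's objective for this endpoint (section 3) is worded "Assess the effects of treatment with darolutamide vs. enzalutamide on daily activity as assessed by accelerometry", where most of the other functional objectives say compare.

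**The concern.** The SAP treats five covariates as worth adjusting for, then takes its only specified CPM arm comparison from an analysis that uses none of them, not even baseline CPM or the randomization stratum. Its CMH and log-rank comparisons do use the age stratum.

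A change score fixes the slope on baseline at 1. Fitting the slope is never less precise in large samples, and is more precise when the true slope differs from 1. At stake are the width of the confidence interval and the power for the CPM comparison. A report would also show adjusted means by arm beside an unadjusted difference, possibly on another scale, with the choice of headline result left open until data are in hand.

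**Working it through.** **The plan's own figure.** The only power statement is for the TUG endpoint: about 120 randomized, 10% drop-out, 20% vs 40%, one-sided 10%, 85% power. With 120 × 0.9 = 108, or 54 per arm:

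z = [0.20·√54 − 1.2816·√(2·0.3·0.7)] / √(0.2·0.8 + 0.4·0.6) = (1.470 − 0.831)/0.632 = 1.01, so power is 0.844. The figure reproduces. Nothing comparable is stated for CPM, so 54 per arm (N = 108) is carried over as an assumption.

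**Variance formulas.** Let k be follow-up SD over baseline SD and rho the baseline-to-visit correlation. In units of baseline variance:

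- change score: 1 + k² − 2·rho·k
- adjusted for baseline: k²(1 − rho²)
- cost of fitting p covariates: (N − 3)/(N − 3 − p), which is 105/100 = 1.05 for the full planned model (p = 5) and 105/103 = 1.019 for baseline + age (p = 2)

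Covariates other than baseline are taken as non-prognostic, which is the unfavourable case for adjustment. The values of rho and k are assumptions.

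| k | rho | Change score | Adjusted | Ratio | Full model | Baseline + age |
|---|---|---|---|---|---|---|
| 1.0 | 0.5 | 1.00 | 0.75 | 0.750 | 0.788 | 0.765 |
| 1.0 | 0.7 | 0.60 | 0.51 | 0.850 | 0.892 | 0.867 |
| 1.0 | 0.9 | 0.20 | 0.19 | 0.950 | 0.997 | 0.968 |
| 1.2 | 0.5 | 1.24 | 1.08 | 0.871 | 0.915 | 0.888 |
| 1.2 | 0.7 | 0.76 | 0.734 | 0.966 | 1.015 | 0.985 |
| 0.9 | 0.5 | 0.91 | 0.608 | 0.668 | 0.701 | 0.681 |
| 0.9 | 0.7 | 0.55 | 0.413 | 0.751 | 0.789 | 0.766 |
| 0.9 | 0.9 | 0.19 | 0.154 | 0.810 | 0.850 | 0.826 |

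The true slope is rho·k. Where it equals 1, adjustment for baseline gains nothing and only the fitting cost remains: 5% of variance for the full model and 2% for baseline + age. A simulation of the full model with equal SDs (6,000 trials per rho) gave ratios of 0.786, 0.904 and 0.999 at rho 0.5, 0.7 and 0.9, in line with the formula.

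**Confidence interval.** Width scales with the square root of the ratio. With equal SDs, baseline + age narrows it by about 13% (√0.765 = 0.874), 7% (√0.867 = 0.931) and 2% (√0.968 = 0.984) at rho 0.5, 0.7 and 0.9.

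**Power.** Assumptions: two-sided 5%, 54 per arm, equal SDs, log-SD 0.4 to 0.5. One case by hand, for a 20% effect at log-SD 0.4 and rho 0.5: the t-test SE is 0.4·√(2/54) = 0.0770, and ln 1.2 / 0.0770 = 2.37, giving power of about 0.65. The full model's SE is 0.0770·√0.788 = 0.0683, and the quotient 2.67 gives about 0.75.

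Simulated power at a 20% effect (10,000 trials per setting, lognormal CPM), log t-test to log full model:

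- log-SD 0.4: 0.652 to 0.763 at rho 0.5; 0.865 to 0.901 at rho 0.7
- log-SD 0.5: 0.479 to 0.575 at rho 0.5; 0.677 to 0.726 at rho 0.7

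That is about 10–11 points at rho 0.5 and 4–5 at rho 0.7. At rho 0.9 there is no gain, but power there is already 0.99 or more.

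At a 10% effect (noncentral t, same comparison):

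- log-SD 0.4: 0.232 to 0.282 at rho 0.5; 0.353 to 0.388 at rho 0.7
- log-SD 0.5: 0.164 to 0.196 at rho 0.5; 0.244 to 0.268 at rho 0.7

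That is about 3–5 and 2–3.5 points.

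On untransformed CPM, which keeps the protocol's mean-change endpoint, baseline + age at a 20% effect moves simulated power as follows:

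- log-SD 0.4: 0.638 to 0.731 at rho 0.5; 0.846 to 0.873 at rho 0.7
- log-SD 0.5: 0.445 to 0.523 at rho 0.5; 0.624 to 0.662 at rho 0.7

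That is 8–9 and 3–4 points, with none at rho 0.9.

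Type I error was 0.046–0.052 for the t-tests and 0.045–0.054 for the adjusted models.

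**Fewer evaluable participants.** The SAP requires that "Subjects must provide at least 2 out of 7 days of data prior to the visit", so CPM may be evaluable in fewer than 54 per arm. At an assumed 42 per arm, with equal SDs and a 20% effect, the full log model still adds 9–10 points at rho 0.5 and about 5 at rho 0.7.

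**The case against.** The strongest reply is that nothing here is wrong. The SAP applies the test that the protocol names to the endpoint that the protocol names. Randomization makes that comparison valid. The endpoint is secondary, unpowered and tied to an objective of assessment. All of this stands, and a reader who inferred that the t-test is biased or invalid would go beyond the documents.

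Second, the adjusted model is already planned and the SAP does not rule out a contrast from it. That also stands: the gap is one unspecified output. Nor does the SAP rank its CPM analyses. The t-test is the main comparison only in the sense that it alone is given an arm difference, interval and p-value.

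Third, the gain is not established. A reader might infer a sure gain at rho 0.5 to 0.7 and none near 0.9. The documents give no rho, and those thresholds hold only for equal SDs: at k = 1.2 the full model loses slightly at rho 0.7, and at k = 0.9 it gains 15% of variance at rho 0.9. The power gain also depends on the assumed effect.

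Fourth, because the SAP calls CPM skewed, a reader might infer that the log-scale contrast should replace the mean-change result. That would turn the protocol's difference in mean change into a ratio of geometric means. Skewness supports reporting the log contrast as well, not substituting it.

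Finally, SAP 3.1 makes the randomized phase conditional, with endpoint and sample size to be reassessed, so 54 per arm may not stand. That makes the sizes provisional, but it also means the wording can be changed before randomization begins.

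**Conclusion.** The point holds as one of efficiency and specification. The only specified CPM arm comparison ignores baseline CPM and the age stratum, its scale is unstated, and the planned adjusted model is not asked for a contrast.

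With 54 per arm, equal SDs and null additional covariates, the full planned model cuts variance by about 21% at rho 0.5 and 11% at rho 0.7, and by essentially nothing at 0.9. Baseline + age does slightly better throughout (ratios 0.765, 0.867 and 0.968). With unequal SDs the full-model ratio runs from 0.70 (k = 0.9, rho 0.5) to 1.01 (k = 1.2, rho 0.7). The most that can be lost is about 5% of variance for the full model and 2% for baseline + age. If the other covariates are prognostic, the full model does better than shown.

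The reading of the text is secure. The size of the benefit is not, since rho, k and the effect are all assumed. The primary TUG analysis is unaffected.

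**What to change.** For the randomized phase, amend SAP 5.5.2 (Daily Activity) as follows.

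1. State the scale of the t-test.
2. At each visit, report the darolutamide vs enzalutamide contrast (estimate, 95% CI, p-value) from a model for change in CPM adjusted for baseline CPM and the age stratum. Fit it on the mean-change scale so that the protocol endpoint is kept.
3. Name that contrast as the main CPM comparison before the randomized phase starts.
4. Add the matching contrast from the already planned adjusted percent-change (log-scale) model as a further result.
5. Keep the t-test as supportive, matching protocol 9.4.2.
6. Record the change in SAP 6.0, which now reports none.

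Lead-in CPM data can supply rho and the SD ratio to check the assumptions, bearing in mind that they come from about 30 participants on darolutamide only.

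The cost is SAP wording, one small model, one contrast from a model already planned and one entry in SAP 6.0; no new data are needed. The downsides are a departure from the test named in the protocol, and a gain that may be nil, or a loss of up to about 2% of variance, if the true baseline slope is near 1.

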### Cognitive function

- The proportion of participants with a decline in cognitive function at 24 and within 52 weeks as assessed by HVLTR, TMT, and COWA, will be summarized. At each assessment, the change in score from baseline will be calculated and the status of cognitive function will be categorized as improved, stable, or declined using the Reliable Change Index (RCI) as shown below. Each test will be assessed individually. The proportion of participants with a decline and exact 95% CIs will be summarized. For the randomization phase, the proportion of subjects with a decline will be summarized separately by treatment arm, and a comparison between arms at week 24 and week 52 will be made using CMH test adjusting for Age (<75, ≥75).

Test	Reliable Change Index threshold (from baseline)
Hopkins Verbal Learning Test - Revised Total Recall (HVLTR TR)	±5 words HVLTR TR has a range of 0-36, recalling a list of 12 words over 3 trials.
Hopkins Verbal Learning Test - Revised Delayed Recall (HVLTR DR)	±3 words HVLTR DR has a range of 0-12.
Hopkins Verbal Learning Test - Revised Delayed Recognition (HVLTR RECOG)	±2 words HVLTR RECOG has a range of -12 to 12 words. It is equal to true positives (subject says 'yes' to 12 original words on list) minus false positives (subjects says 'yes' to distractors [12 words not on original list]).
Trail Making Test: Part A (TMTA)	±12 seconds TMT Part A is timed up to a maximum of 3 minutes. If not completed in the given amount of time, the subject is assigned a time equal to the maximum time.
Trail Making Test: Part B (TMTB)	±26 seconds

	TMT Part B is timed up to a maximum of 5 minutes. If not completed in the given amount of time, the subject is assigned a time equal to the maximum time.
Controlled Oral Word Association (COWA)	±12 words Subjects are asked to name as many words as possible all beginning with a specified letter. A total of three trials are administered, and the score on the COWA is the total number of words named across the three trials.

- The proportion of participants with a decline of >10 points from baseline in the FACT-Cog domain at 24 and within 52 weeks will be summarized in a similar fashion.

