Treatment dispensing / accountability			X	←=====→									
AE review ^b			←=====→										
AEs of interest review, including fall ^c			←=====→										
Timed Up and Go assessment (TUG) ^d	X ^h		X ^h			X	X		X	X			
Short Physical Performance Battery (SPPB) ^d			X			X	X		X	X			
Accelerometry assessment ^e	X					X	X		X	X			
Cognitive function ^f			X				X		X	X			
Brief Fatigue Inventory (BFI) ^g			X	X	X	X	X		X				
Patient Health Questionnaire (PHQ-9)			X	X	X	X	X		X	X			
Survival status												X	

X = measure/action to be performed at the time point indicated

←=====→ = measure/action to be performed continually during the time period indicated

AE = adverse event; BFI = Brief Fatigue Inventory; COWA = Controlled Oral Word Association; CRF = case report form; HVLTR = Hopkins Verbal Learning Test - Revised; PHQ-9 = Patient health questionnaire-9; PSA = prostate-specific antigen; SPPB = Short Physical Performance Battery; TMT = Trail Making Test; TUG = Timed Up and Go

- a PSA will be assessed at the same time as other laboratory assessments. A time window of ± 14 days is allowed for laboratory and PSA assessments.
- b Including survival, pain, radiographic progression, metastases, and skeletal events
- c AEs of interest are fractures, falls, and hypothyroidism
- d Physical function tests include SPPB and the TUG assessment.
- e Accelerometry assessment will require the participant to wear an accelerometry device on the wrist or hip for a minimum of 7 days at each time point. The first accelerometry assessment is to be performed before the first dose (i.e. during screening).
- f Cognitive function tests include the HVLTR, TMT, and COWA, as well as the patient-reported outcome questionnaire FACT-Cog.
- g BFI is a 5 minute self-assessment tool that identifies fatigue in cancer participants over a 24-hour period.
- h The first TUG assessment is to be performed before the first dose (either during screening or Week 1 Day 1).
- i Once the baseline procedures are completed, the first administration of study intervention will be provided at the study center and the participant will be provided with additional medication to take as scheduled through the Week 4 visit. (Each participant will be instructed to bring any remaining drug back to the center at the Week 4 visit.)

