
The secondary objectives of this study are to:
 
 
• Compare the effects of treatment with darolutamide vs. enzalutamide on physical function, as assessed by the TUG test at 12 and 24 weeks, and by 52 weeks.
 
• Compare the effects of treatment with darolutamide vs. enzalutamide on physical function as assessed by Short Physical Performance Battery (SPPB) test at 12 and 24 weeks, and by 24 and 52 weeks.
 
• Assess the effects of treatment with darolutamide vs. enzalutamide on daily activity as assessed by accelerometry at 12 and 24 weeks, and by 24 and 52 weeks.
 
• Compare the effects of treatment with darolutamide vs. enzalutamide on cognitive function as assessed by Hopkins Verbal Learning Test-Revised
 
	
Physical Function:
 
 
• Proportion of participants with an increase of at least 1 second in TUG time at 12 and 24 weeks and during the 52 weeks from baseline, using the best TUG time out of the measured assessments during study visits.
 
• Time to worsening (increase of at least 1 second) in TUG time.
 
• Proportion of participants with a worsening in SPPB total score at 12 and 24 weeks and during the 24 weeks and 52 weeks from baseline. Worsening is defined as one point worsening in SPPB total score from baseline.
 
 
Daily Activity:
 
 
• Mean change from baseline in daily physical activity at 12 and 24 weeks, and during the 24 weeks and 52 weeks from baseline.
 
• Mean change from baseline in accelerometer-assessed proportion of time spent in light to vigorous physical activity (light physical activity defined as 100<AC per minute<760 and moderate-to-vigorous activity (≥760 AC per minute), at 12 and 24 weeks, and during the 24 weeks and 52 weeks from baseline.
 
 
Cognitive Function:
 
 
• Proportion of participants with a decline in cognitive function during the 24 weeks and 52 weeks from baseline, as assessed by HVLt-R, TMT, and COWA. See Table 4 for the definition of decline for each test.
 

Objectives	Endpoints

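### The 52-week cognitive endpoint counts a decline at any time, but the SAP words its between-arm test by visit, so the test may use Week 52 status instead

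*SAP*

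**What the plan says.** The endpoint is a period endpoint in both documents. Protocol section 3 and SAP Table 1 give it as "Proportion of participants with a decline in cognitive function during the 24 weeks and 52 weeks from baseline". Protocol 9.4.2 plans to summarise the proportion "with a decline in cognitive function by 24 and 52 weeks" in the same way as the primary endpoint, which includes a Cochran-Mantel-Haenszel (CMH) comparison of the arms.

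The cognitive function bullet in SAP 5.5.2 opens with the proportion "with a decline in cognitive function at 24 and within 52 weeks". Later in the same bullet, for the randomized phase, "a comparison between arms at week 24 and week 52 will be made using CMH test", adjusted for age group. FACT-Cog follows in a second bullet and is to be handled in the same manner.

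Four other provisions bear on the point:
- The schedules of activities place cognitive tests at Week 1 Day 1, Week 24, Week 52 and then in active follow-up.
- SAP Table 3 includes anyone with a baseline and one later assessment on the instrument.
- The missing-data rule for endpoints in SAP 4.2 covers the Timed Up and Go (TUG) endpoint only.
- SAP 6.0 declares no change from the planned analyses.

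**The concern.** The endpoint asks whether a man declined at either of two assessments. The comparison sentence, taken at its word, asks whether he was in decline at the second one. These are different outcomes, and they also admit different men to the analysis.

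The SAP does not make the choice, and this is an open-label trial. If the choice is left to programming, it may be made after data have been seen. The report could then print a within-52-week proportion for each arm beside a p-value for something else, and a reader could not tell.

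**Working it through.** **1. Where the two readings differ.** Up to Week 24 there is one scheduled post-baseline cognitive test, so decline at Week 24 and decline by Week 24 are the same. Up to Week 52 there are two tests:

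| Week 24 | Week 52 | Any decline up to Week 52 | Status at Week 52 |
|---|---|---|---|
| Declined | Declined | Event | Event |
| Not declined | Declined | Event | Event |
| Declined | Not declined | Event | Non-event |
| Declined | No test | Event | No value |
| Not declined | Not declined | Non-event | Non-event |
| Not declined | No test | Needs a rule | No value |

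Rows three and four are where a defined event is lost. Table 3 would keep the man in row four; a Week 52 status test has no value for him.

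**2. The plan's only power figure.** It is for TUG: 20% against 40%, one-sided alpha 10%, about 120 men, 10% drop-out, 85% power. With 120 × 0.9 = 108 evaluable, or 54 per arm, a pooled-variance two-proportion test without continuity correction gives 84.4%. That reproduces the figure. No rate, alpha or power is stated for cognition, so what follows is illustration at 54 per arm and one-sided 10%, unstratified.

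**3. Size of the difference in the reported rate.** Let p24 and p52 be the single-visit decline rates, b the probability of decline at both, and l the share lost after Week 24, independently of decline. Then

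any-time rate = p24 + (1 − l) × (p52 − b).

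Assume 15% and 30% at each visit, normal change scores with correlation 0.5, and l = 10%. Then b is 0.0577 and 0.1568.
- Lower-rate arm: 0.15 + 0.9 × (0.15 − 0.0577) = 23.3%.
- Higher-rate arm: 0.30 + 0.9 × (0.30 − 0.1568) = 42.9%.

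The gaps from Week 52 status are 8 and 13 points. Over single-visit rates of 10% to 40% and correlations of 0.3 to 0.7, the gap is about 5 to 18 points per arm.

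**4. Effect on power.** In the first three rows correlation is 0.5 and l = 10%, so Week 52 status has 54 × 0.9 = 48.6 men per arm. The other rows assume no loss. In the fourth, half of the Week 24 declines persist, so b = 0.5 × p24. In the last, a lasting true decline is joined by a 10% chance of a false decline at each visit in both arms.

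| Assumed decline rates | Week 52 status | Any time up to Week 52 |
|---|---|---|
| 15% v 30% at both visits | 69% | 82% |
| 15% v 15% at Week 24, 15% v 30% at Week 52 | 69% | 47% |
| 15% v 20% at Week 24, 15% v 35% at Week 52 | 85% | 73% |
| 20% v 40% at Week 24, 20% v 30% at Week 52 | 47% | 80% |
| Lasting 20% v 40%, plus false declines | 75% | 66% |

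For the last row, Week 52 rates are 0.20 + 0.80 × 0.10 = 28% and 0.40 + 0.60 × 0.10 = 46%. The chance of at least one false decline in two visits is 1 − 0.9² = 0.19, so the any-time rates are 0.20 + 0.80 × 0.19 = 35.2% and 0.40 + 0.60 × 0.19 = 51.4%.

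Any-time counting gains power when the effect is similar at both visits or larger early. It loses power when the effect comes late or false declines are common.

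**The case against.** The strongest reply is that no mismatch exists. The bullet has already defined its proportion as decline within 52 weeks, the comparison sentence concerns that same proportion, and the named weeks may only mark the two analysis horizons. The neighbouring fatigue bullets apply CMH to period proportions. This reading is possible, so nobody can say that the SAP definitely tests Week 52 status. But elsewhere in 5.5.2 the SAP separates results at a visit from results at any time up to a week, and the fatigue comparison names no week. By the SAP's own usage the literal reading is by visit, and a programmer could reasonably code it so.

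A reader might also infer that the wording costs power. The documents do not support that: they give no cognitive rates, and the direction reverses under plausible assumptions.

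Nor does everyone who stops treatment leave the comparison. Protocol 7.1 keeps men who discontinue study drug under evaluation for 52 weeks. Those at issue withdrew from follow-up, died, were lost or missed the visit.

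Finally, this is one of many secondary comparisons, and SAP 3.1 makes the randomized phase conditional, with its endpoint and time frame still to be chosen. That limits the consequence without removing the need for one definition.

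**Conclusion.** The point holds as an inconsistency of definition. The endpoint is cumulative in Protocol section 3, Protocol 9.4.2 and SAP Table 1, while the comparison is worded by visit. Followed literally, the 52-week p-value would belong to a different outcome and a different set of men from the endpoint and the proportion reported with it.

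The any-time rate exceeds the Week 52 rate unless essentially all Week 24 declines persist and no decliner is lost. The 5 to 18 points rest on assumed rates, normal change scores and 10% random loss; none of these is a cognitive figure from the documents.

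The Week 24 comparison is unaffected. FACT-Cog carries the same ambiguity by cross-reference and is not a separate error. No claim about power, in either direction, follows from the documents.

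**What to change.** In SAP 5.5.2, reword the sentence containing "a comparison between arms at week 24 and week 52 will be made using CMH test" so that the age-adjusted CMH test compares (a) the proportion with a decline at Week 24 and (b) the proportion with a decline at any assessment up to Week 52, that is, at Week 24 or Week 52.

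Add a rule for a missing Week 52 test. Under (b), a man with a Week 24 decline is already an event. The rule must say how a man without one is counted, and whether death is treated differently from a missed visit.

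Apply the same text to FACT-Cog. Keep Week 52 visit status as a descriptive summary.

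The cost is a sentence or two of SAP wording, with no new data and no change to the visit schedule. It restores the endpoint that both documents already define, and should be made before any randomized-phase data are examined.
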